12.1 Activities Required Prior to Initiation of the Study

12.1.1 Clinical Trial Agreement (CTA) and Financial Arrangements

A fully executed (signed by all required parties) CTA must be on file with the Sponsor prior to any investigator participating in this study. This agreement must explain the financial arrangement with the investigative site.

12.1.2 Institutional Review Board/Ethics Committee Protocol Approval

This study protocol must be submitted to and approved by the Investigator's Institutional Review Board (IRB) or Ethics Committee (EC). A copy of the IRB or EC approval letter must

be submitted to the Sponsor. The letter should identify the following:

- Protocol name and/or number.
- Date of IRB or EC meeting (if available).
- Date of approval.
- Date of expiration.
- Signature of IRB or EC.

12.1.3 Clinicaltrials.gov Registration

The Sponsor will be responsible for registering this study on www.ClinicalTrials.gov if required by local and national regulations.

12.2 Clinical Data Collection Submission

12.2.1 Summary of Case Report Form Data Collection

Study data will be collected on source documents which may include study-specific worksheets provided by the Sponsor. For subjects having bilateral SCP procedure, separate case report forms must be completed for each operative side.

The following source document and/or CRF completion guidelines should be followed:

- Complete carefully and accurately.
- Complete header information consistently across all case report forms for each individual study subject (when study-specific source document and/or CRFs are used).
- Be sure that data on the source documents match that which is entered through the electronic data capture (EDC) system.
- Use the study subject's unique Case ID number assigned as instructed. Do not provide information that is not requested on the source document and/or CRFs.
- Ensure that all fields are completed. For fields completed by the subject, efforts should be made to obtain any missing responses prior to the subject completing their visit.
- Source document and/or CRFs are to be completed with permanent black or blue ink.
- Do not overwrite, obscure, or whiteout an incorrect entry. To correct an error, draw a single line through the incorrect entry, add the correct entry next to it, and initial and date the correction. Corrections must be initialed and dated as they are made.
- Any change or correction to a Source Document and/or CRF should be dated, initialed, and explained (if necessary) and should not obscure the original entry in accordance ICH E6(R2) guidelines.
- The source document and/or CRFs should be easily readable.

12.2.2 Data Submission

Data will be submitted using an electronic case report form (eCRF) platform. If there is missing or out-of-range information, the system will give immediate feedback to the individual

making the entry and allow for correction and/or the assignment of a data query.

Investigative study sites will be asked to enter subject data into the eCRFs no later than 2 weeks from the time the subject was seen for their scheduled study visit.

Submitted forms will undergo review by Zimmer Biomet personnel and questions or requests for corrections will be sent to the site via the EDCs electronic data query system. All corrections are to be made by a member of the study staff within the EDC system as well as any needed corrections to paper CRFs following GCP guidelines. Zimmer Biomet personnel will review corrected information in the study database.

12.2.3 Quality Assurance of Data

The Investigator should ensure the accuracy, completeness, legibility, and timeliness of the data reported to the Sponsor in the CRFs and in all required reports. Data reported on the source document CRF, which are derived from source documents, should be consistent with the source documents or the discrepancies should be explained. All electronic systems used to create, modify, maintain, or transmit electronic study records will be validated. The Sponsor will maintain quality control systems, in accordance with the Sponsor's policies and procedures.

12.2.4 Patient Privacy and Identification

All personally identifiable information on the source document CRFs, as well as on any additional self-assessment form, will be pseudonymized in accordance with regional and/or national data privacy protection laws/regulations.

The collection and processing of personal data from subjects enrolled in this study will be limited to those data that are necessary to investigate the efficacy, safety, quality, and utility of the investigational product(s) used in this study.

The processing of personal data will comply with applicable data privacy protection laws and regulations, and all information will be treated with strict adherence to professional standards of confidentiality. Zimmer Biomet has put measures in place to ensure an adequate level of protection for the data irrespective of the country where it is transferred. All personnel in the data management team will comply with applicable data privacy protection laws and regulations.

Measures to ensure appropriate data protection are detailed in the ICFs provided and explained by participating Investigators to each participant.

12.2.5 Data Management

Investigators and their teams will collect and enter the data in a FDA 21 CFR Part 11 Compliant central database system managed by the Sponsor or third party in contractual relationship with the Sponsor. Data analysis will be conducted by internal statisticians on pseudonymized data. The database will be subjected to quality control checks and the resulting output will be used to generate data queries. Data queries will be used to record and to document the recovery of incomplete, inconsistent, or missing data.

Data is to be recorded utilizing subjects' source documentation, which includes medical records, operative and clinic notes, ancillary services reports, subject surveys and in some cases Case Report Forms. The subject-completed surveys are considered source documentation for this information. This may include electronically collected ePRO surveys where the direct data entry of survey data by the subject constitutes electronic source, paper surveys completed and submitted by the subject, or paper surveys completed on behalf of the subject by the site coordinator during phone interviews. Case Report Forms or certified copies of Case Report Forms may also serve as source documentation when the information is in addition to what is typically entered into a subject's medical record (e.g., fields documenting SCP time on the Surgical Documentation Form). Any Case Report Forms used as source documentation are to be labeled as such and made part of the subjects' case histories. Data are to be recorded accurately and in a timely manner following each event.

Questions regarding the content of the forms should be directed to the Zimmer Biomet Study Representatives.

Data analysis will be conducted by internal statisticians on pseudonymized data. The database will be subjected to quality control checks and the resulting output will be used to generate data queries. Data queries will be used to record and to document the recovery of incomplete, inconsistent, or missing data.

Each participating Investigator will receive periodic study reports on their own pseudonymized data as well as pseudonymized data for the whole study group. Anonymized study metrics, e.g. summary tables, graphical output and descriptive statistics will be produced and may be available as hard copy. Strict confidentiality of individual hospital data will be maintained.

12.3 Reporting Requirements

12.3.1 Investigator Reporting Responsibilities

The Investigator should ensure the accuracy, completeness, legibility, and timeliness of data reported to the Sponsor in accordance with this protocol. The Investigator or Designee will provide periodic reports to their IRB or EC as required to maintain IRB or EC approval throughout the study, and will provide any required final reporting to the IRB or EC upon study completion/termination. A copy of all IRB or EC re-approval letters must be submitted to the Sponsor. If the IRB or EC terminates or suspends its approval of the study, the Investigator or Designee will suspend study-related activities and will promptly notify the Sponsor. The Investigator should also promptly provide written reports to the Sponsor and the IRB or EC regarding any changes significantly affecting the conduct of the study, and/or increasing risk to the subjects.

12.3.2 Retention of Records

Study records must be retained by the Investigator or Designee for a minimum of 15 years from the Investigator's study termination date, or per applicable regulatory and/or IRB or EC requirements (whichever time period is greater). Measures shall be taken to prevent

accidental or premature destruction.

Study records are defined as the all information in original records, certified copies of original records of clinical findings, observations or other activities in a clinical study, including source data initially recorded in an electronic format, necessary for the reconstruction and evaluation of the clinical study. This may include but is not limited to: hospital records, clinic records, laboratory notes, device accountability records, photographs, radiographs, subject casebooks, regulatory records, signed informed consents and all other study-related documents

12.4 Management of Intercurrent Events

12.4.1 Failure to Obtain Informed Consent

Study participation will be offered at the time of the pre-operative visit at the hospital. Patients willing to participate in the study will be presented with the informed consent. Study data will not be collected until the Informed Consent has been signed and dated by the candidate. If a candidate does not wish to participate (does not sign and date the Informed Consent), data for that candidate will not be collected for this study.

12.4.2 Revision

In the event that revision of the SCP surgical site in the index hip is necessary, the Investigator will determine the best treatment and/or revision method for the subject. Once the revision surgery has been completed, the Investigator or qualified Designee must complete a **Serious Adverse Event** form and a **Study Exit** form.

12.4.3 Investigator Withdrawal

The Investigator can choose to withdraw a subject from the study if it is deemed to be in the subject's best interest or the subject does not consent to continue in the study after being informed of changes in the research that might affect them. The reason for the Investigator's withdrawal of the subject must be documented on the **Study Completion** case report form.

12.4.4 Subject Withdrawal

Study participation may be discontinued through surgical conversion (Total Hip Arthroplasty or total removal of AccuFill), withdrawal of consent, Investigator decision or death. A subject may voluntarily withdraw their consent from the study at any time without prejudice or affecting their future medical treatment. Investigators may withdraw a subject due to non-compliance with the protocol or follow-up questionnaire schedule, or for reasons of medical discretion.

All consented subjects who are withdrawn/ discontinued from the study should have an End of Study form completed to explain why they are no longer participating in the study.

When a subject withdraws or is withdrawn, all study procedures completed and data collected prior to the date of withdrawal will be submitted to the sponsor and included in the study database, unless the subject requests otherwise in writing.

Should a subject who previously chose to withdraw wish to re-enter the study, a new Informed Consent will be required. The site may resume scheduled follow-up visits from the subject's last follow-up visit.

12.4.5 Lost to Follow-up

Although follow-up compliance is essential to study quality, some subjects may not be able to complete follow-up evaluations. If the subject does not complete the required questionnaires through the two year time point and the Investigator or a member of the study staff has attempted to contact that subject at least three times (with any combination of an email reminder via EDC system, a phone call or an IRB approved subject follow-up letter) and receives no response, the subject may be deemed to be lost to follow-up. The research staff will document the attempts to contact the subject. The final attempt to contact the subject will be performed by register/return receipt mail. The receipt will be placed in the subject's binder. An End of Study/Withdrawal Form must be completed.

Should a subject expire, complete the Adverse Event and End of Study/Withdrawal Form. Submit copies of the death certificate, autopsy report (if applicable and available) and source documents related to the death. The Investigator will make written notification to the IRB upon the death of a subject in the study, based on the individual IRB requirements.

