10.3 Number of Cases and Maximum Enrollment per Investigation Site

A total number of approximately 50 subjects across 15 sites in the United States.

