11.7 Follow-up Procedures

In order to minimize the burden to patient and physician, patients will be enrolled at the physician's office, but will not be required to come back to the office for follow-up visits.

A Numeric Pain Score will be collected at the first post-operative standard of care visit at approximately 7-21 days.

Thereafter, subjects complete self-reported outcomes measures post-operatively at 6 weeks, 12 weeks, 6 months, 1 year and 2 years. These measures include:

- Use of pain medication and therapy
- Subject-reported outcomes:
 - Numeric Pain Scale
 - Modified Harris Hip Score
 - Hip Outcome Score
 - EQ-5D
 - Subject Global Satisfaction Survey

The post-operative visit data must be collected for each enrolled subject via email, in-person, regular mail or telephone (with an IRB approved phone script). If the subject is not seen in person, a member of the study staff will contact the subject by telephone at the aforementioned time points to inquire about their outcomes, any conversion surgeries, and adverse events.

Follow-up evaluations are detailed in Table 1— Schedule of Events. Follow-up is to occur within the windows described in Table 1.

The study database will be configured to send an email notification to subjects at the beginning of each specified visit window with a reminder that they need to complete the surveys. This email will contain a method to allow the subjects to complete their surveys electronically via the database's electronic Patient Reported Outcomes (ePRO) system.

Prior to contacting the study subject to assess potential adverse events by telephone, a member of the study staff will check to confirm whether these surveys have been completed electronically or not. If the subject has not completed the evaluation yet, a member of the study staff will ask if the subject would like to complete the questionnaires by phone, email or if they would like a copy of the surveys to be mailed out to them. Mailed surveys will be sent with a stamped, return envelope. The subject should be instructed to return the surveys within one week and to include the date of completion at the top of any of the pages. Any subject survey forms that are not collected via the database's ePRO system are to be maintained in the subjects' study files as source documents.

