16.1 Sample Size Calculation

The sample size required is based on the overall group mean improvement of the Harris Hip Score by at least the minimal clinically important differences (MCID) of 18.0 points from baseline to one year.

Based on internal Zimmer Biomet studies, assuming an improvement from baseline of 31.4 points with a standard deviation of 22.4, 80% power and alpha set at 0.05, 24 patients are needed to show the mean improvement from baseline is greater than the MCID of 18.0. Considering an attrition rate of 25%, 32 patients should be enrolled in the study. At an enrollment rate of approximately 50 subjects the study is more than adequately powered to show improvement over the MCID.

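### For subjects who stop responding, the plan requires no check of the site's own record before closure, so their conversion and adverse-event status is left unknown and its handling unstated

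*Combined protocol and SAP*

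**What the plan says.** **How events are found.** Section 11.7 does not oblige subjects to return to the office. Outcome forms may be completed electronically, by post, by telephone or in person. Where there is no in-person visit, "a member of the study staff will contact the subject by telephone at the aforementioned time points to inquire about their outcomes", together with conversion surgery and adverse events. The Synopsis says the same. Section 10.4 adds that screening for both continues throughout the study, but names no other method.

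**What happens when contact fails.** Section 12.4.5 applies when questionnaires are not completed through two years and at least three contact attempts have failed. If the site "receives no response, the subject may be deemed to be lost to follow-up". The last attempt is by registered mail, and an End of Study/Withdrawal form follows. Section 11.8 offers a letter and the use of additional contacts as optional steps, and allows closure after three consecutive missed visits with failed contact. All of these steps are attempts to reach the subject. None is a search for surgical or safety status.

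**What the record is used for.** Section 12.2.5 says data are recorded from "source documentation, which includes medical records, operative and clinic notes", among other sources. Section 11.4 uses the record for the history of subjects enrolled after surgery, and 11.8 has contact attempts logged in it. No section links it to the event status of a non-responder.

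**How events are reported.** Section 16.3 summarises complications as frequencies with percentages. It gives no denominator, no censoring rule and no category for unknown status.

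**The concern.** Section 10.7 makes confirmation of long-term safety an objective, and 10.7.1 places adverse-event incidence under the primary endpoint. Under 11.9 and 12.4.2 a revision leads to a Serious Adverse Event form and exit, but only if the site learns of it. A subject who has had a hip replacement, or is dissatisfied, has little reason to keep answering questionnaires about the index procedure. It is therefore plausible, though the documents do not show it, that silent subjects have more events than responders.

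The missing questionnaire score of a silent subject cannot be recovered. Surgical and safety status often can, because the operating site may hold the note. A plan followed exactly as written can close such a subject with the event sitting in its own chart. At stake is the credibility of the adverse-event and conversion percentages in a study of about 50 subjects, where a handful of unrecorded events changes the result visibly.

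**Working it through.** **1. Where the 25% comes from.** Section 16.1 sizes the study for a Harris Hip Score change above the "minimal clinically important differences (MCID) of 18.0 points from baseline to one year", "assuming an improvement from baseline of 31.4 points with a standard deviation of 22.4, 80% power and alpha set at 0.05". The difference is 31.4 − 18.0 = 13.4 with SD 22.4. A two-sided one-sample t-test at 0.05 reaches power 0.801 at n = 24, which agrees with "24 patients are needed to show the mean improvement from baseline is greater than the MCID of 18.0". The plan does not state sidedness; a one-sided t-test would need 19. Then 24 / (1 − 0.25) = 32, which agrees with "Considering an attrition rate of 25%, 32 patients should be enrolled in the study". The plan's figures reproduce. They also show what the 25% is: an allowance for a score analysis at one year.

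**2. Number of subjects, for illustration.** Target enrolment is 50 (Section 10.3: "A total number of approximately 50 subjects across 15 sites in the United States"). 0.25 × 50 = 12.5, so 12 or 13 subjects of unknown status and 38 or 37 observed.

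**3. Formulas.** Let L be the fraction lost before any event is recorded, p the event rate in responders and q the rate in the lost.

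- True rate = (1 − L)p + Lq
- Reported over all enrolled = (1 − L)p, too low by Lq
- Reported over observed = p, too low by L(q − p)

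**4. Results for L = 25% and p = 20% (assumed).**

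| Assumed q in the lost | True rate | Over all enrolled | Over observed |
|---|---|---|---|
| 0% | 0.75 × 20% = 15% | 15% | 20% |
| 20% | 15% + 5% = 20% | 15% | 20% |
| 40% | 15% + 10% = 25% | 15% | 20% |
| 100% | 15% + 25% = 40% | 15% | 20% |

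When q exceeds p, both denominators understate. When q equals p, only the all-enrolled figure does. When q is below p, the observed figure is too high. Both shortfalls are proportional to L: at half the loss (12.5%) with q = 40%, they are 5 and 2.5 points instead of 10 and 5.

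**5. Width of the uncertainty.** The only event rate in the documents is 30% at two years, from a knee study (Section 6.1), used here purely as an example of an observed rate.

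- 12 lost: 0.30 × 38 = 11.4 expected events. None of the lost failed: 11.4/50 = 22.8%. All failed: 23.4/50 = 46.8%.
- 13 lost: 0.30 × 37 = 11.1 expected events. None failed: 11.1/50 = 22.2%. All failed: 24.1/50 = 48.2%.

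The choice of denominator does not narrow this range of about 22% to 48%. Finding the status of the lost subjects does.

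**The case against.** Several points on the other side stand.

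- A reader might infer that failures among the lost are counted as event-free. The documents do not say so. Section 16.3 fixes no denominator, and its reference to crude rates concerns return to function and outcome measures. Over observed subjects the automatic dilution disappears, and bias remains only if the lost differ from responders.
- A reader might take 25% as the expected share of silent subjects at two years. It is a one-year sizing allowance and may include deaths, withdrawals and subjects who left at conversion or revision, whose events are known.
- A reader might treat the 10-point shortfall in the example as a ceiling. It is not: if every lost subject had failed, the true rate would be 40% against 15%.
- A record check is omitted, not forbidden. The closure rule is permissive, and staff are in the chart when logging contact attempts. In-person contact remains possible, including the first standard-of-care visit at about 7 to 21 days. Section 10.6 mentions physical examinations, and 6.4.3 and 15.1 mention post-operative monitoring of the surgical site.
- A conversion rate is not a named endpoint; adverse-event incidence is.
- The consent statement in Section 14 covers access for monitoring and regulatory audit. It does not establish that sites may collect new outcome data on non-responders.

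None of this supplies the missing step. General statements about screening and monitoring do not say what to do for a subject who cannot be reached. Section 14 makes source checks optional and centres them on the operative report. The arithmetic applies equally to any yes/no safety event, including those under 10.7.1.

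**Conclusion.** The point holds as an ascertainment gap. For subjects not seen in person, events are sought by asking them. For those who do not answer, the plan requires contact attempts only, and it says nothing on how unknown status enters the percentages. It cannot be said that the plan scores these subjects as successes, or that a quarter of them will be lost.

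In the illustration, a true 25% would be reported as 15% over all enrolled or 20% over observed. This rests on an assumed 20% in responders and 40% in the lost, on a borrowed 25% loss, and on all of that loss having no recorded event. The actual effect could be smaller or larger. It is a worthwhile low-cost improvement to a descriptive single-arm study and not a flaw that invalidates it.

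**What to change.** - **Sections 11.8 and 12.4.5.** Before a subject is closed as lost, and at the two-year point for non-responders, the site checks its own hospital and clinic record for conversion, reoperation or revision, and device- or procedure-related events. It enters status and last-known date on CRF 10 and, where an event is found, CRF 11. The check stays within the scope of the signed consent and leaves out subjects who have withdrawn it. The sponsor should confirm that the consent form covers this use.
- **Section 16.3.** State the denominator for adverse-event and conversion percentages, show subjects of unknown status as a separate line, and give a best/worst-case range with none or all of them having the event.
- **Closure triggers.** Reconcile 11.8 (three consecutive missed visits) with 12.4.5 (questionnaires not completed through two years) in the same amendment.

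The cost is minutes of chart review per lost subject by existing staff, 12 or 13 charts at the illustrative 25%, with no added visits. Surgery done at another hospital may still be missed, so the check narrows the gap without closing it.
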